10.1.2 Serious Adverse Events

A summary of incidence rates (frequencies and percentages) of SAEs by treatment group, SOC, and preferred term will be prepared for the Safety population. A data listing of SAEs will also be provided, displaying details of the event(s) captured on the CRF.

10.1.3 Deaths

A listing of deaths will also be provided for the Safety Population.

10.2 Clinical Laboratory Evaluations

Laboratory data include analyses for Chemistry and Hematology and will be summarized by treatment and visit for the Safety Population. Descriptive summaries of actual values and changes from each baseline will be presented by study visit and each treatment group. 95% confidence intervals will be presented for change from each baseline for each visit. ET data will be analyzed with the closest visit that does not have a valid assessment value.

Laboratory values will be displayed in the data listings and those that are outside the normal range (“H” or “L”) will be flagged, along with corresponding normal ranges. Values pre-defined as potentially clinically significant (“HH” or “LL”) will also be flagged. For each laboratory analysis, shifts in assessments of abnormality from each baseline to each scheduled time point will be presented in shift tables.

A by-participant listing of all clinical laboratory data will also be provided.

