9.6. Unscheduled Visits

Patients may need to be seen at other times than the scheduled study visits for additional safety assessments or to follow-up, as medically necessary, on clinical laboratory, physical examination, or other findings. In addition, if a patient calls between scheduled visits to report a visible lesion in the oral cavity or other concerning oral cavity AE, the patient should be asked to return to the clinic as soon as possible for an unscheduled oral cavity examination. If an additional study visit occurs, the date and nature of the visit will be documented in the CRF and in the source documents.

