10.3.1.5. Clinical Laboratory Assessments

The clinical laboratory evaluations to be performed in this study are listed in [Table 2](#). All tests will be performed at Baseline (Visit 1) and after 12 weeks of treatment (Visit 5), or Early Termination.

With the exception of the urine pregnancy tests, all clinical laboratory evaluations will be analyzed via a central clinical laboratory, and information regarding appropriate sample volume, collection tubes, sample labeling and handling, and shipment will be provided in a study manual. Each clinically significant abnormal laboratory value or other clinically meaningful abnormality should be followed until the abnormality resolves or until a decision is made that it is not likely to resolve. If such abnormalities do not return to normal within a reasonable period, their etiology should be identified and Tonix or designee should be notified. Treatment-emergent clinically significant abnormalities in laboratory values will be recorded as AEs.

Table 2: Clinical Laboratory Assessments

Clinical chemistry	Hematology
Alanine aminotransferase (ALT)	Hematocrit
Alkaline phosphatase	Hemoglobin
Aspartate aminotransferase (AST)	MCH concentration (MCHC)
Bilirubin (total)	Mean corpuscular hemoglobin (MCH)
Blood urea nitrogen (BUN)	Mean corpuscular volume (MCV)
Calcium	Platelet count
Chloride	Red blood cell (RBC) count
Cholesterol (total)	WBC differential
Creatine kinase (CK)	Neutrophil count (absolute and %)
Creatinine	Lymphocyte count (absolute and %)
Glucose	Monocyte count (absolute and %)
Phosphorus	Eosinophil count (absolute and %)
Potassium	Basophil count (absolute and %)
Protein (albumin and total)	White blood cell (WBC) count
Sodium	
Urine Pregnancy Test (qualitative dipstick) ^a	

^a Pregnancy testing for females of child-bearing potential only. A positive pregnancy test mandates withdrawal from the study (all visits).

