2. STUDY OBJECTIVES AND ENDPOINTS

2.1 Study Objectives

2.1.1 Primary Objective

The primary objective of the study is to evaluate the safety of TNX-102 SL taken daily at bedtime over an additional 12 weeks in patients with PTSD who have completed a double-blind lead-in study.

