5. SAMPLE SIZE DETERMINATION

No sample size calculations were made for this study as it is a follow-on, open-label study. The sample size for this study will depend upon the number of patients who complete the lead-in study, remain eligible for entry, and indicate willingness to participate in this extension study.

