10.4 Vital Signs

Descriptive summaries (mean, SD, median, minimum, and maximum) of actual values and changes from each baseline at each assessment time point and last on-treatment assessment will be calculated for vital signs including weight, BMI, body temperature, pulse rate, systolic blood pressure and diastolic blood pressure. 95% confidence intervals will be presented for change from each baseline.

These summaries will be presented by treatment and assessment time for the Safety population. ET data will be analyzed with the closest visit that does not have a valid assessment value.

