10.5 Visual Examination of Oral Cavity

A visual examination of the oral cavity will be assessed at Baseline and Week 12. A visual examination is to be done any time a participant spontaneously reports an oral adverse event (aside from AEs known to be sensory-only, such as numbness, tingling or bitter taste) to confirm presence or absence of any signs of irritation or other visible

abnormalities. A data listing of the visual examination results performed at each scheduled visit and at the time of an adverse event will be presented.

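### In a study whose primary objective is safety, marked individual changes are counted only if recorded as an AE or, for laboratory tests, if they show as a category shift at a scheduled or ET time point

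*SAP*

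**What the plan says.** SAP 2.1.1 sets the aim: "The primary objective of the study is to evaluate the safety of TNX-102 SL". The objective measures are then handled as follows.

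- **Laboratory schedule (Protocol 10.3.1.5).** "All tests will be performed at Baseline (Visit 1) and after 12 weeks of treatment (Visit 5), or Early Termination". Only one post-baseline draw is planned.
- **Unscheduled visits (Protocol 9.6).** "Patients may need to be seen at other times than the scheduled study visits for additional safety assessments", and follow-up of laboratory findings is among the stated reasons.
- **Laboratory analysis (SAP 10.2).** There are descriptive summaries with confidence intervals, and "shifts in assessments of abnormality from each baseline to each scheduled time point will be presented in shift tables". "Values pre-defined as potentially clinically significant" (HH or LL) are flagged, in the paragraph that describes the listings. No table of patients with such a value is named, and the limits are not printed. ET results go to the nearest visit that lacks a valid value. All laboratory data are listed by participant.
- **Vital signs (SAP 10.4).** "Descriptive summaries (mean, SD, median, minimum, and maximum) of actual values and changes from each baseline at each assessment time point", together with the last on-treatment assessment and 95% confidence intervals for change.
- **Oral examination (SAP 10.5).** "A data listing of the visual examination results performed at each scheduled visit and at the time of an adverse event" is the only output. The opening of SAP 10 names this examination among the data to be summarised.
- **Adverse events.** Protocol 10.3.1.5 and 12.1 direct that clinically significant abnormalities be recorded as AEs. SAP 10.1 counts AEs by system organ class and preferred term, with separate tables for oral cavity AEs and their characteristics.

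**The concern.** Unscheduled draws tend to happen because something looked wrong, so they are where a marked value is most likely to be seen. The shift table is built around one planned time point and does not look for the worst value. The other route to a count is the AE record, which depends on a judgement of clinical significance. The protocol does not define that judgement, and each site makes it for itself in an open-label study. The HH/LL limits could give a check that does not depend on the investigator, but no table is said to use them.

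The signals are plausible. The package insert in Protocol Appendix 3 lists tachycardia, changes in blood pressure and weight, abnormal liver function, stomatitis, and tongue swelling and discolouration. The oral examination is the direct local check for a sublingual tablet. Because it is done routinely at Week 12, it can find a lesion in a patient who reported nothing.

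At stake is whether the study report can say how many patients, out of how many assessed and by lead-in group, had a marked change. A listing gives neither numerator nor denominator.

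**Working it through.** The plan states no figure on this point, so the check sets the sections side by side.

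| Measure | Route to a patient count | Shown without a patient count |
|---|---|---|
| Laboratory | Category shift at a scheduled or ET time point (SAP 10.2); AE, if judged clinically significant (SAP 10.1) | HH/LL flags at any time; unscheduled values (listing) |
| Vital signs | AE, if judged clinically significant | Mean, SD, median, minimum, maximum (SAP 10.4) |
| Oral examination | Oral cavity AE (SAP 10.1) | Examination findings (listing, SAP 10.5) |
| C-SSRS | Any on-treatment event; ideation at its worst response (SAP 10.3) | – |

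**Step 1: a transient laboratory abnormality.** Take a hypothetical patient who is normal at both baselines, HH at an unscheduled draw on Day 40 (an assumed day) and normal at Week 12. The shift table runs to the scheduled point, so the entry is normal-to-normal. The HH flag appears in the listing. An AE is counted only if the investigator judged the value clinically significant.

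**Step 2: does the visit-window rule rescue the value?** SAP 7.1.2 splits the time between visits at the midpoint. Within a window it takes the record nearest the target date, preferring a scheduled visit only in a tie. The rule sits under a heading on discontinuation and withdrawal, so it may not apply here. If it does, on the protocol's day count:

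- Week 4/Week 8 boundary: (28 + 56)/2 = Day 42.
- Week 8/Week 12 boundary: (56 + 84)/2 = Day 70.
- The Day 40 value falls before Day 42, in the Week 4 window. No laboratory test is scheduled at Week 4, so a table running to scheduled laboratory points has no place for it.
- An unscheduled draw on Day 75 (also assumed) falls in the Week 12 window, 84 − 75 = 9 days from target. A Week 12 draw made within its ±7 days is always closer and is used instead.

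The rule selects by nearness, not by severity, so the gap remains on either reading.

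**Step 3: vital signs.** The maximum change at a visit is the same whether one patient or several reached it. Minimum and maximum therefore show that an extreme occurred, not how many patients had one.

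**Step 4: oral examination.** SAP 10 promises summaries and SAP 10.5 delivers a listing. Protocol 12.1 names the examination findings as a safety measure separate from AEs. The oral AE tables cannot show how many patients were examined or how many became abnormal.

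**Step 5: consistency.** For the C-SSRS the SAP already counts patients with any on-treatment event and takes the worst ideation response. The same logic is not applied to the other three measures.

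**The case against.** The strongest reply is that the plan already captures most of what matters. Clinically significant abnormalities become AEs at any visit and are tabulated with percentages. Shift tables are themselves counts of individual changes, and ET values enter them. A large vital-sign change would be visible as the maximum and would widen the SD. Oral AEs have their own incidence and characteristics tables, and an extra oral examination is triggered by an oral AE that is already counted. All laboratory values are listed. The proposed tables fulfil no explicit protocol commitment beyond the endpoint statistics and flagged listings in Protocol 12.1.

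Most of that stands, and it rules out three stronger readings that a reader might infer:

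- **Marked changes are never counted.** The AE tables and the scheduled or ET shifts do count some of them.
- **Unscheduled laboratory results are barred outright.** SAP 10.2 does not say so, and SAP 7.1.2 leaves room for an unscheduled record to enter a window.
- **Vital signs are reduced to means.** Median, minimum, maximum and last on-treatment values are also planned.

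Nor is it stated whether the shift categories include HH and LL. The limits are described as pre-defined and may be held in another document.

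The reply does not supply a count that is independent of the investigator's judgement for three things: any-time HH/LL values, extreme vital signs, and abnormal findings at a routine oral examination. Nor does it reconcile SAP 10 with SAP 10.5 on the oral examination.

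**Conclusion.** The point holds as a gap in reporting. Marked individual changes reach a table of counts only through an AE record or, for laboratory tests, through a category shift at a scheduled or ET time point. A transient unscheduled laboratory abnormality that is not judged clinically significant would appear only in a listing.

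The size cannot be put in patients. SAP 5 says "No sample size calculations were made for this study as it is a follow-on, open-label study", and the documents give no abnormality rates and no expected number of unscheduled draws. A reader might infer that the safety conclusion will be too favourable; the documents do not show that. They show only that the planned tables could miss such changes.

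The conclusion rests on two assumptions: that the shift tables are produced as worded in SAP 10.2, and that no separate output specification adds outlier tables. It is a cheap improvement, worth making because safety is the primary objective.

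**What to change.** 1. **SAP 10.2.** Keep the scheduled shift table. Add a shift from each baseline to the worst on-treatment value after the first open-label dose, using scheduled, unscheduled and ET results. Add a table of the number and percentage of patients with any post-baseline HH or LL value, using the limits already pre-defined, and print those limits. State whether the shift categories include HH and LL, and whether the SAP 7.1.2 window rule applies to unscheduled results.
2. **SAP 10.4.** Add counts of patients with values or changes beyond reporting limits fixed before database lock. The documents supply no such limits, so the sponsor must set and document them.
3. **SAP 10.5.** Add a baseline versus worst post-baseline oral examination table (normal/abnormal), which would also meet the promise in SAP 10.
4. **Denominators.** Use patients with at least one post-baseline value of the measure. The default in SAP 7.1 is everyone in the treatment group, including patients never reassessed.
5. **On-treatment.** Say how an ET value obtained after a lapse in dosing is classed, since Protocol 9.5 allows for such visits.

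The cost is a few extra tables by lead-in group and no new data. Counts may look slightly less favourable than the present summaries. Patients with more draws have more chances of an abnormal worst value, which is why the scheduled shift table should stay beside the new one.

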10.3 Columbia Suicide Severity Rating Scale (C-SSRS)

The C-SSRS is an instrument that measures suicidal ideation and behavior. Items measuring suicidal ideation and suicidal behavior are displayed in the table below. Frequency counts of yes/no responses to items below and whether any suicidal ideation or behavior is present will be summarized as described below.

The overall number of participants with any suicidal ideation or behavior (by type and in total) or self-injurious behavior while on-treatment will be provided by treatment group. For ideation, participants will only be counted once at each visit and/or time frame at the worst case response for ideation type (1-5), where 1 is the least severe and 5 is the most severe type of ideation.

Category	Items
A) Suicidal Ideation	(1) Type 1: Wish to be dead (2) Type 2: Non-specific active suicidal thoughts (3) Type 3: Active suicidal ideation with any methods (not plan) without intent to act (4) Type 4: Active suicidal ideation with any some intent to act, without specific plan (5) Type 5: Active suicidal ideation with specific plan and intent
B) Suicidal Behavior	(1) Preparatory acts or behavior (2) Aborted attempt (3) Interrupted attempt (4) Actual attempt (5) Completed suicide Suicidal Behavior present (composite of items 1-5) Non-Suicidal Self-Injurious Behavior

Suicidal intensity of ideation will be calculated by tallying up the five intensity items to create a total score ranging 0-25. If a participant does not have any suicidal ideation, a score of 0 will be given. Separate tables will be created for the entire Safety Population as well as the population comprising only participants exhibiting any suicidal ideation. Suicidal intensity of ideation total score will be summarized using descriptive statistics by treatment group.

A data listing of C-SSRS results will include only participants with suicidal ideation, suicidal behavior, or self-injurious behavior without suicidal intent. For participants with suicidal ideation, suicidal behavior, or self-injurious behavior without suicidal intent at any time, data from all visits are displayed.

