Safety data will be summarized by treatment group. Adverse events will be coded using the same version of the Medical Dictionary for Regulatory Activities (MedDRA) as used for the lead-in study and will be summarized overall and by preferred term and system organ class (SOC). Adverse events will also be summarized by severity and relationship to study drug. Serious AEs and AEs leading to discontinuation of study drug will also be summarized. Adverse events that are ongoing at Week 12 from the lead-in study will be transcribed into the eCRF. All other adverse events that are reported after starting TNX-102 SL 5.6 mg in this extension study, or that worsen after entry into the extension study, will be considered newly emergent AEs (NEAEs), even if the type of event was previously reported (and resolved) during the lead-in study.

Actual values and changes from both baselines for clinical laboratory test results, vital sign measurements, and in the BDI-II score will be summarized at endpoint using descriptive statistics (n, mean, SD, median, minimum, and maximum). The number of patients with baseline and treatment-emergent suicidal ideation and/or suicidal behavior or self-injurious behavior, based on the C-SSRS, will be summarized by treatment group.

Efficacy Analyses:

Descriptive statistics by treatment group and study visit will be displayed for a number of efficacy endpoints, including:

- Change from both baselines in the total CAPS-5 score
- Proportion of patients with a CGI-I score of “very much improved” or “much improved” from both baselines
- Change from both baselines in the SDS total score
- Change from both baselines in the individual items assessed using the SDS
- Change from both baselines in patients’ quality of sleep using the PROMIS Sleep Disturbance scale
- Change from both baselines in CAPS-5 symptom cluster subscores
- Proportion of patients with a $\geq 50\%$ improvement from baseline (both baselines) in total CAPS-5 score
- Change from both baselines in BDI-II score

Hypothesis testing will also be performed on the above efficacy endpoints. Missing values will not be imputed, and no adjustments will be made for multiplicity.

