6.3. Study Endpoints

6.3.1. Safety

Safety will be assessed by:

- Adverse events (AE) and serious AEs (SAEs) throughout the entire duration of the study, including assessment of AEs involving the oral cavity
- Changes from both baselines in clinical laboratory test results
- Changes from both baselines indicative of increased suicidal ideation or behavior as assessed by the Columbia Suicide Severity Rating Scale (C-SSRS)
- Change from both baselines in BDI-II
- Changes from both baselines in vital signs and weight

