12.1. Evaluation of Safety

Safety will be assessed by the monitoring and recording of AEs, clinical laboratory tests, vital signs, visual examination of the oral cavity findings, the monitoring of suicidality using the Columbia C-SSRS scale, and patient-rated assessments of depressive symptomology (BDI-II).

Adverse events will be coded using the Medical Dictionary for Regulatory Activities (MedDRA) and will be summarized overall and by preferred term and system organ class. Adverse events will also be summarized by severity and relationship to study drug. Serious AEs and AEs leading to discontinuation of study drug will also be summarized.

Actual values and changes from the extension study baseline values for clinical laboratory test results and vital sign measurements will be summarized at endpoint using descriptive statistics (n, mean, standard deviation (SD), median, minimum, and maximum). Laboratory values will be displayed in the data listings along with corresponding normal ranges, and those that are outside the normal range will be flagged.

Based on the C-SSRS results, the frequency and severity of suicidal ideation and behavior will be tabulated at each time point. The number of patients with baseline and treatment-emergent suicidal ideation and/or suicidal behavior or self-injurious behavior, based on the C-SSRS, will be summarized by treatment group.

All data gathered will be listed by patient and parameter, and clinically significant abnormalities should be recorded as AEs.

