2.2.2 Safety Endpoints

Safety will be assessed by:

- Adverse events (AE) and serious AEs (SAEs) throughout the entire duration of the study, including detailed assessment of AEs involving the oral cavity.
- Changes from both baselines in clinical laboratory test results.
- Changes from both baselines in vital signs and weight.
- Change from both baselines in BDI-II.
- Suicidal ideation or behavior as reported on the Columbia Suicide Severity Rating Scale (C-SSRS).

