7.3 Safety Assessments

Safety will be assessed by:

- AE and SAEs throughout the entire duration of the study, including detailed assessment of AEs involving the oral cavity.
- Changes from both baselines in clinical laboratory test results.
- Changes from both baselines in vital signs and weight.
- Change from both baselines in BDI-II (see [Section 7.2.4](#)).
- Suicidal ideation or behavior as assessed by the C-SSRS.

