8.3 Demographics and Other Baseline Characteristics

Descriptive summaries of the demographic and other baseline characteristics will be completed for all participants in the safety population by treatment groups, unless otherwise specified.

Descriptive summaries of demographic and other baseline conditions will include:

- Demographics (age, gender, race/ethnicity, height, weight, body mass index (BMI), family status, education, presence of current MDE, current nicotine, alcohol and THC usage, and employment status). In addition to the safety population, these will also be repeated for all randomized participants and the mITT population.
- CAPS-5 Assessment (Diagnostic version)

Other assessment’s baseline values will be reported with their respective follow-up measures.

Medical History will be coded using Medical Dictionary for Regulatory Activities (MedDRA) version 19.0 and summarized by System Organ Class (SOC) and Preferred Term using frequency counts by treatment group. Note that the medical history is collected in the lead-in study; this analysis displays that information for the population of subjects that entered this study.

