12. CHANGES FROM PLANNED ANALYSIS

Study day as it appears in data listings and the Study Data Tabulation Model (SDTM) and Analysis Data Model (ADaM) datasets will differ from the protocol: The protocol describes the day of first dose as "Day 0"; the listings and datasets will conform to the standard of first dose day appearing as "Day 1".

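### SAP 10.3 omits the treatment-emergent C-SSRS count that the protocol promises, gives no definition of emergence, and SAP 12 does not declare the change

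*SAP*

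**What the plan says.** The protocol makes the commitment in three places. The synopsis (Safety Analyses) promises a by-group summary of this quantity: "The number of patients with baseline and treatment-emergent suicidal ideation and/or suicidal behavior or self-injurious behavior, based on the C-SSRS". Section 12.1 repeats the promise. Section 6.3.1 lists the endpoint itself as a change: "Changes from both baselines indicative of increased suicidal ideation or behavior as assessed by the Columbia Suicide Severity Rating Scale (C-SSRS").

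The SAP words it differently. Sections 2.2.2 and 7.3 keep the reference to both baselines for laboratory tests, vital signs with weight, and the BDI-II. For the C-SSRS the endpoint becomes "Suicidal ideation or behavior as reported on the Columbia Suicide Severity Rating Scale (C-SSRS") in 2.2.2 and "Suicidal ideation or behavior as assessed by the C-SSRS" in 7.3. Section 10.3 then plans this, by treatment group: "The overall number of participants with any suicidal ideation or behavior (by type and in total) or self-injurious behavior while on-treatment will be provided". Ideation is counted once per visit or time frame at its worst type. There is also a 0-25 intensity score, and a listing of all visits for affected participants.

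SAP 12 has a single entry, which begins "Study day as it appears in data listings and the Study Data Tabulation Model (SDTM") and concerns only whether the first dose day is called Day 0 or Day 1.

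**The concern.** Being on treatment when ideation is reported does not make the ideation treatment-emergent. A patient with type 1 ideation at the end of the lead-in and the same type 1 ideation at Week 4 is counted under SAP 10.3 in the same row as a patient whose ideation began after the first open-label dose. The protocol's count is meant to separate the two.

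Safety is the primary objective and suicidality is a named safety measure, so the C-SSRS summary is not peripheral. The choice of baseline also matters. For patients who had placebo in the lead-in, the P303 baseline is the one that precedes first exposure to TNX-102 SL. For patients who continue on active drug, only the P301 baseline does. With no baseline named and no rule written, two analysts could report different emergent counts from the same data, and the rule would be chosen after the data are seen.

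**Working it through.** The documents give no C-SSRS counts, so there is no figure in the plan to reproduce. The check has two parts.

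**Part 1: commitments against plan**

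| Item | Protocol | SAP |
|---|---|---|
| Endpoint | Increase from both baselines (6.3.1) | Presence, as reported or assessed (2.2.2, 7.3) |
| By-visit frequency and severity | Yes (12.1) | Yes, worst type per visit (10.3) |
| Treatment-emergent patient count by group | Yes (synopsis, 12.1) | None |
| Definition of emergence for the C-SSRS | None; 12 defers full analysis detail to the SAP | None |
| Declared as a change | n/a | No (12) |

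Protocol 12.1 asks for the by-visit tabulation and then, separately, for the emergent count. The SAP's by-visit tables meet the first request and not the second. The SAP does handle the same problem elsewhere: 10.1 defines newly emergent adverse events as new or worsened, and 10.2 plans laboratory shift tables from each baseline. The gap is specific to the C-SSRS.

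**Part 2: can the planned counts be turned into the promised one?**

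SAP 8.3 says that other assessments' "baseline values will be reported with their respective follow-up measures", so a baseline C-SSRS row may well be printed. Let N be the patients in a group, B those with ideation at baseline and T those with ideation on treatment. The number with new-onset ideation can lie anywhere between

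- lower limit: max(0, T − B)
- upper limit: min(T, N − B)

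The illustration below assumes N = 100 per group and types 1-3 only. Patients with type 0, 1, 2, 3 are given in that order.

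| Baseline | On treatment | B | T | Lower limit | Upper limit |
|---|---|---|---|---|---|
| 95, 3, 1, 1 | same | 5 | 5 | max(0, 0) = 0 | min(5, 95) = 5 |
| 90, 6, 3, 1 | same | 10 | 10 | max(0, 0) = 0 | min(10, 90) = 10 |
| 80, 12, 6, 2 | same | 20 | 20 | max(0, 0) = 0 | min(20, 80) = 20 |
| 90, 6, 3, 1 | 85, 9, 4, 2 | 10 | 15 | max(0, 5) = 5 | min(15, 90) = 15 |

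The ranges are the same if a rise in type among patients already positive is counted as well as new onset. In the last row, the lower limit is reached when five patients move from 0 (three to type 1, one to type 2, one to type 3) and nobody else changes. The upper limit is reached when all 15 on-treatment cases come from the 90 without ideation at baseline.

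**Which categories are exposed**

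Protocol 10.3.1.2 says that scores of 4 or 5 should be reported as serious adverse events, and SAP 10.1.2 tabulates those by group. That leaves 5 − 2 = 3 ideation types (1, 2 and 3) with no score-based route into any summary table outside SAP 10.3. Behavior is less affected: the since-last-visit form (Protocol 10.3.1.1) makes on-treatment behavior counts close to counts of events in the treatment period. Inclusion criterion 4 makes a lead-in increase with plan or intent unlikely at P303 baseline.

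**The case against.** The strongest reply is that the SAP is less bare than it looks. SAP 10 lists the C-SSRS among the safety data and says that continuous parameters will be summarized with change from baseline as appropriate, so change in the intensity score is plausibly planned. A significant C-SSRS change indicating greater risk is to be recorded as an adverse event. Newly emergent events are tabulated by preferred term, and suicidal ideation is also among the abuse-related terms in SAP Appendix 3. The protocol never defines treatment-emergent for the C-SSRS, so on-treatment counts beside baseline values could be the SAP's version of the promised pair. The listing and analysis datasets allow the count to be programmed, and no efficacy inference is touched.

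Part of this stands. The protocol leaves the term undefined, the data are not lost, and the ranges above are generic arithmetic on assumed counts. The SAE table is also not limited to new cases. A worst value over several visits compared with one baseline value leans toward showing an increase, and the documents do not give the C-SSRS version or recall period at the P301 baseline.

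The rest does not answer the point. A mean change in intensity is not a patient count. The adverse event route captures only what someone judged significant, which is weakest for types 1-3. Protocol 6.3.1 speaks of increase from both baselines, which mere presence on treatment does not measure. Being able to program a count later is not the same as having specified it.

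**Conclusion.** The concern holds. A by-group safety summary that the protocol promises under its primary objective is missing from the SAP, with no definition to rebuild it from and no declared change. As written, the C-SSRS tables do not separate new or worsened ideation from persisting ideation, and adding a baseline column would not recover the number: in the assumed examples the uncertainty spans 5 to 20 patients per 100. The practical reach is mainly ideation types 1-3. The conclusion about the text rests on no assumption; only the illustrative ranges depend on assumed counts. This should be corrected before database lock. It does not threaten the study, because the data are scheduled and patient-level listings are planned.

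**What to change.** In SAP 2.2.2, 7.3 and 10.3, restore the number of patients with treatment-emergent ideation, suicidal behavior or self-injurious behavior, by treatment group. Define the term against each named baseline (P301 and P303), for example as a worst on-treatment ideation type higher than at that baseline, or behavior not present at that baseline. State the recall period of each baseline assessment and how a worst value over several visits is compared with a single baseline value. Confirm in 10.3 that baseline counts are shown alongside. A table of baseline type by worst on-treatment type is a convenient layout, though the protocol does not require it. If the omission is intended, declare and justify it in SAP 12.

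The cost is SAP wording and one or two tables. The C-SSRS is already scheduled at Visits 1-5 (Protocol Appendix 1). The lead-in baseline values are needed as well, and Protocol 6.3.1 already presupposes them.
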